13.4 Sample Size

13.4.1 Accrual Estimates

This is a single institution, phase II study to evaluate the safety and efficacy of fractionated stereotactic body radiation therapy in subjects with unresectable or locally recurrent pancreatic or periampullary cancer. The study will recruit two cohorts of patients; one will be patients who had recurrent or residual disease after previous chemoradiation therapy (Cohort A), and the other will be patients who had recurrent or residual disease after surgery and/or chemotherapy without radiation (Cohort B). Cohort A will be treated with 5 Gy x 5 for palliative retreatment, and Cohort B will be given 6.6 Gy x 5 for definitive treatment. We anticipate recruiting 2-3 patients per month for each cohort.

13.4.2 Sample Size Justification

The primary goal of this study is to access the late gastrointestinal toxicity rates including grade 2 or greater gastritis, fistula, or ulcer and any other grade 3 or greater gastrointestinal toxicity in Linac based SBRT patients. Two cohorts will be accrued in this study; one will be patients who recurrent or residual disease after previous chemoradiation therapy (Cohort A), and the other will be patients who had recurrent or residual disease after surgery and/or chemotherapy without radiation (Cohort B). Cohort A will be treated with 5 Gy x 5 for palliative retreatment, and Cohort B will be given 6.6 Gy x 5 for definitive treatment. Two cohorts will be evaluated separately.

The sample size is 60 patients per cohort. The primary outcome used to determine the sample size is the percentage of individuals with a late gastrointestinal toxicity (grade 2-4) at one year. The late grade 2 or greater toxicity rates was previously observed for other treatment regiments for locally advanced pancreatic cancer were approximately 40%. We hypothesize that in each cohort, the toxicity rate for this regimen will be 20%, a 50% reduction. The stopping rules for futility were calculated based upon a two-stage design with a total sample size of 60 and an interim analysis of 16 patients (note: accrual will continue while interim analysis is being conducted). Within 16 patients, if 7 or more patients have late grade 2 or greater gastritis, enteritis, fistula, ulcer, or late grade 3 or greater GI toxicity, the trial will be stopped. If 6 or fewer patients have late grade 2 or greater gastritis, enteritis, fistula, ulcer, or late grade 3 or greater GI toxicity, then the study will continue enrolling patients until 60 patients have been accrued. After 60 patients are enrolled, if 17 or more of the patients have late grade 2 or greater gastritis, enteritis, fistula, ulcer, or late grade 3 or greater GI toxicity, the null hypothesis will not be rejected. If 16 or fewer of the patients have late grade 2 or greater gastritis, enteritis, fistula, ulcer, or late grade 3 or greater GI toxicity, we will conclude that one year late toxicity is below 40%. This design will reach 91% power with 2% type I error for grade 2 or greater late toxicity, and the probability of early termination is 0.47. In addition, this sample size will reach 89% and 90% power to test the increase of 1-year local progression free survival from 30% to 45% in cohort A and 50% to 65% in cohort B, respectively.

The calculation is based on a one-sided test at significance level 0.04, assuming exponential distribution for local progression time and 2.5 year uniform accrual time with 1 year follow up.

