3.2 Rationale for Fractionated Stereotactic Radiotherapy

The mortality rate for pancreatic cancer approaches 100%. Current therapies provide only partial palliation of symptoms and slight prolongation of survival. More effective therapies are clearly needed. Several clinical trials have shown that Linac based SBRT has the potential to significantly improve progression-free survival of patients with pancreatic tumors, which could translate into both more effective palliation and longer patient survival.

Koong *et al.* previously used the CyberknifeTM stereotactic radiosurgery system to demonstrate that a single dose of 25 Gy Linac based stereotactic body radiotherapy (SBRT) was feasible for patients with locally advanced pancreatic cancer (36). Furthermore, this dose of radiation resulted in near 100% progression free survival and effectively palliated symptoms related to the local growth of pancreatic tumors. Based on this study, the same group also completed a phase II study assessing the efficacy of combining a standard five-week course of chemoradiotherapy followed by a stereotactic radiosurgery boost to the primary tumor in patients with locally advanced pancreatic cancer. In this cohort of 19 patients, 100% of tumors were without local progression. However, all patients eventually developed metastases, with a median time to progression of 5.5 weeks.

More recently, another phase II study treated locally advanced pancreatic cancer patients with gemcitabine followed by 25 Gy of Linac based SBRT delivered with Cyberknife and maintenance gemcitabine chemotherapy. In this study, the excellent progression free survival was confirmed from previous studies (81%). The median overall survival was 11.4 months, median time to progression was 9.7 months and the 1 year survival was 50% (37). There were no significant acute GI toxicities however, of the 15 patients alive >6 months after Linac based SBRT, 7 (47%) experienced Grade 2 or greater GI toxicity, with 2 (13%) of the 15 experiencing Grade 3 or greater GI toxicity.

Linac based SBRT is delivered using linear accelerators and image-guided radiation therapy (IGRT). These machines combine a conventional high-energy linear accelerator with a kV imager capable of volumetric, cone beam CT (CBCT). Because of these innovations, it is possible to deliver highly accurate, stereotactic radiation treatments.

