A recent protocol evaluated full dose gemcitabine before and after single fraction Linac based SBRT. Preliminary results indicate that the local progression free survival was comparable to what was previously observed (90%) with CyberKnife treatment (personal communication). All acute toxicity was grade 2 or less; however, a minority of patients developed late duodenal ulcers (15%), including 1 perforation (5%) with a single fraction of Linac based SBRT. Therefore, LInac based SBRT appears to achieve local control of

pancreatic tumors in a large majority of patients with reasonable rates of toxicity, suggesting that Linac based SBRT would be an effective treatment option for patients with locally recurrent disease, as we propose in this protocol.

To date, Stanford has treated more than 150 patients with Linac based SBRT, and this treatment has resulted in local control rates of >90% with acceptable acute GI toxicity. We predict that this treatment will not adversely impact patients' quality of life. Although QOL measures have not been thoroughly studied among pancreatic cancer patients treated with Linac based SBRT, the majority of patients treated with Linac based SBRT appear to derive a clinical benefit as assessed by decreased pain, decreased fatigue, and increased weight. A single fraction of Linac based SBRT (25 Gy x 1) has resulted in excellent tumor control. However, close to 50% of these patients developed late duodenal toxicity within one year, primarily because of the proximity of the duodenum to the pancreas.

We hypothesize that delivering fractionated Linac based SBRT (5 Gy x 5 or 6.6 Gy x 5) instead of single fraction treatment will result in equivalent tumor control with less late toxicity ($\leq 20\%$). At this time, there is no clear consensus regarding an optimal fractionation schedule for unresectable pancreas cancer (38,39). Based on a recent study, this fractionation schedule is predicted to provide equivalent tumor control probability to 25 Gy x 1 while resulting in less normal tissue toxicity (40).

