Two recent studies support this assertion. In 2009, Chang *et al.* reported on the use of Linac based SBRT delivered as 25 Gy in a single fraction for patients with unresectable pancreatic adenocarcinoma (67). Of the 77 patients, 58% had locally advanced disease and 14% had medically inoperable disease, but the remainder were similar to our population in that they had either low-burden metastatic disease (19%) or locally recurrent disease (8%). Results were encouraging, with rates of freedom from local progression at 6 and 12 months of 91% and 84%, respectively. Overall survival at 6 and 12 months was 56% and 21%, respectively. Only 5% of patients experienced grade 2 or greater acute toxicity, 4% experienced grade 2 late toxicity, and 9% experienced grade 3 or greater late toxicity. Rates of grade 2 or greater late toxicity were 11% and 25% at 6 and 12 months, respectively.

In 2010, Didolkar *et al.* reported on the use of Linac based SBRT doses ranging from 15 to 30 Gy delivered in 3 equal fractions, with mean dose of 25.5 Gy over 3 days (66). Eighty-five patients were studied; the majority (71 patients) had locally advanced disease, but a small number (14 patients) were included who were similar to our population in that they had locally recurrent disease. Results were again encouraging, with 78 patients (92%) achieving complete response, partial response, or stable disease for a duration of 3-36 months with a

median of 8 months. Pain relief was noted in the vast majority of patients lasting for 18-24 weeks. Median survival from time of Linac based SBRT was 8.65 months, which is comparable to or better than reported results for locally advanced pancreatic cancer (69-72). Nineteen patients (22.4%) developed grade 3-4 gastrointestinal toxicity, consisting of duodenitis, gastritis, and diarrhea in order of decreasing frequency. One patient developed renal failure.

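### The primary toxicity count treats patients who die, withdraw or are lost event-free before month 12 as toxicity-free, and the plan does not say whether its 40% benchmark was measured the same way

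*Combined protocol and SAP*

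**What the plan says.** Section 13.4.2 sizes each cohort on "the percentage of individuals with a late gastrointestinal toxicity (grade 2-4) at one year". The null rate is 40% and the hypothesised rate 20%. With 7 or more events in 16 patients the trial stops. "If 16 or fewer of the patients have late grade 2 or greater gastritis, enteritis, fistula, ulcer", or late grade 3 or greater GI toxicity, after 60 are enrolled, the conclusion is that one-year late toxicity is below 40%. Stated properties are 91% power, 2% type I error and a 0.47 probability of early termination. Section 12.2 repeats the interim rule, with a one-year window.

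The 40% is attributed only to earlier experience: rates with "other treatment regiments for locally advanced pancreatic cancer were approximately 40" per cent. No citation, denominator or estimator is given.

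On who is counted:
- Section 13.2 defines a population for efficacy only.
- Section 11.1.1 makes patients evaluable for toxicity at the follow-up visits, with no rule for those who do not reach them.
- Section 6.5 provides only survival follow-up after removal or withdrawal.
- Sections 13.3 and 13.6 plan Kaplan-Meier and competing-risk estimates for survival and local progression. For toxicity they plan tabulation and a grade 3 or higher rate with a 95% CI.

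**The concern.** The test compares an observed count with limits derived from a binomial with rate 40%. That comparison is valid only if the count and the 40% are measured the same way. A patient who dies in month 2 cannot have a late event, yet adds one to the denominator and nothing to the numerator. A patient who withdraws in month 5 may have a later event that nobody records.

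If the 40% came from survivors, or from an actuarial estimate, these patients pull the count down towards 16 or fewer and make the 16-patient stop less likely. The trial could then conclude that toxicity is below 40% when, on the benchmark's own scale, it is not. If the 40% is a crude percentage of all patients from a similarly fatal disease setting, the two sides match. The reader cannot tell which applies. At stake are the meaning of the primary conclusion and its stated error rate.

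**Working it through.** **1. The plan's own figures.** Inputs from section 13.4.2: n1 = 16, stop at 7 or more; n = 60, success at 16 or fewer; rates 0.40 and 0.20.

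P(success | p) = Σ (x = 0 to 6) Bin(x; 16, p) × P[Bin(44, p) ≤ 16 − x]

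- p = 0.40: 0.0209 (stated 2%)
- p = 0.20: 0.9076 (stated 91%)
- early stop, P[Bin(16, 0.40) ≥ 7]: 0.473 (stated 0.47)

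All three reproduce.

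**2. Does the scale matter in this literature?** The background gives late-toxicity figures on different footings:
- Section 3.2: "of the 15 patients alive >6 months after Linac based SBRT, 7 (47%) experienced Grade 2 or greater GI toxicity". This denominator is survivors only.
- Section 3.2, on single-fraction treatment: "close to 50% of these patients developed late duodenal toxicity within one year". This can be read as crude.
- Section 3.3, one single-fraction series: 4% with grade 2 plus 9% with grade 3 or greater late toxicity, so 13% of patients. For the same series, "Rates of grade 2 or greater late toxicity were 11% and 25% at 6 and 12 months, respectively". No estimator is named, but 25/13 ≈ 1.9.

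None of these is identified as the source of the 40%.

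**3. How much under-observation is tolerable?** Suppose a fraction f of the events expected on the benchmark's scale goes unseen through death or loss. The count then follows p = 0.40 × (1 − f). Expected events at f = 0 are 60 × 0.40 = 24.

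| f | Events unseen of 24 | p | Type I error | Early stop |
|---|---|---|---|---|
| 0 | 0 | 0.400 | 2.1% | 0.47 |
| 5% | 1.2 | 0.380 | 4.2% | 0.41 |
| 6.3% | 1.5 | 0.375 | 5.0% | – |
| 10% | 2.4 | 0.360 | 7.9% | 0.34 |
| 12.1% | 2.9 | 0.352 | 10.0% | – |
| 20% | 4.8 | 0.320 | 21.9% | 0.23 |

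This needs no survival model.

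**4. Survival-model scenarios (illustrative only).** Section 3.3 gives one median that runs from SBRT: "Median survival from time of Linac based SBRT was 8.65 months". Assume exponential survival, m = ln 2 / 8.65 = 0.0801 per month, and death independent of toxicity.
- Net 40% with constant hazard over months 3 to 12: h = −ln(0.6)/9 = 0.0568. Then p = h/(h+m) × exp(−3m) × [1 − exp(−9(h+m))] = 0.415 × 0.786 × 0.708 = 0.231, and type I error is 77%.
- The same with no deaths before month 3 (drop exp(−3m)): p = 0.294, type I error 37%.
- 40% among patients alive at month 3, with no earlier deaths: p = 0.40, type I error 2%.

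The answer depends almost entirely on the assumptions.

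**5. Moving the count to patients past month 3.** Expected number = 60 × exp(−3 ln 2 / median). Medians of 7 and 15.9 months give about 45 and 53, though these two medians run from recurrence and from diagnosis. The limits must be re-derived: 13 and 48 evaluable patients with the limits left unchanged gives a type I error of 20.5%. With 16 evaluable patients at the interim and the same interim limit:

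| Final rule | Type I error | Power |
|---|---|---|
| 11 or fewer of 45 | 2.1% | 82% |
| 12 or fewer of 48 | 2.1% | 84% |
| 13 or fewer of 50 | 2.7% | 88% |
| 14 or fewer of 53 | 2.7% | 89% |

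**The case against.** The best defence is that a crude reading is the natural one. Section 13.4.2 speaks of a percentage of individuals, section 7.1 gives its 20% ceiling as a share of patients within one year, and the 20% is called a halving of the 40%, so both are presented on one scale. If the source population had similar mortality and follow-up, the rule is sound. That stands, and it is why the documents show an ambiguity rather than an error.

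It can also be said that death already competes. With everyone followed to month 12 or death, cumulative incidence with death as a competing event equals events divided by N, and section 6.3 plans 12 months of maturation after accrual. That stands too. A reader might infer that the plan ignores competing risk for its primary endpoint. It does not, if event-free death is a deliberate non-event. What is missing is a statement of that convention and any handling of loss and withdrawal.

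Telephone toxicity assessment (section 10) and records from local providers (section 6.4) reduce loss. They are not an analysis rule and do not help after withdrawal, when section 6.5 provides only survival follow-up. Patients removed at planning under section 6.1.3 are a smaller matter: section 13.4.2 frames the outcome in SBRT patients, so they would naturally be left out, although the final count refers to enrolment.

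Safety does not rest on this count alone. Section 12.2 has six-monthly reviews, section 12.1.1 an annual committee review, and section 13.3 allows stopping on recommendation.

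**Conclusion.** The point holds as a gap in definition with a measurable consequence. The stated 2%, 91% and 0.47 are correct for a binomial with full 12-month observation, or for a crude benchmark from patients with similar mortality and follow-up. Outside those cases the margin is thin: about 1.5 unseen events of 24 takes type I error past 5%, about 2.9 past 10%, and at 10% unseen the interim stop falls from 0.47 to 0.34.

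A reader might infer from the survival scenarios that the true type I error is 50% or more. The documents do not support that. Across the medians cited (7 to 15.9 months) and the assumptions tried, the result runs from 2% to 89%. The highest values need a net benchmark, constant hazard, deaths before month 3 despite a life-expectancy criterion above 3 months, and the shortest medians. Only the 8.65-month median is stated to run from SBRT. Nor do the documents show that the 40% is survivor-based.

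**What to change.** 1. State the source and scale of the 40%. If it is crude, keep the count over all SBRT-treated patients and say that death without late toxicity is a non-event; the limits do not change. If it is survivor-based or actuarial, apply the 16- and 60-patient counts to SBRT-treated patients alive and followed beyond month 3, with limits re-derived for the number expected. With an actuarial benchmark, deaths between months 3 and 12 still leave some mismatch, which the restated figures should acknowledge.
2. Do not treat patients lost or withdrawn before month 12 as toxicity-free. For each cohort, report the one-year cumulative incidence of the primary toxicity composite with its 95% CI, censoring loss and withdrawal and treating death as competing. For the same set of patients it differs from the count only through loss and withdrawal.
3. Restate type I error, power and early-termination probability for the chosen set (for example, 12 or fewer of 48 gives 2.1% and 84%). At the least, say that 2%, 91% and 0.47 assume full 12-month observation or a matching crude benchmark.

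The cost is text, one added estimate and somewhat lower stated power if the month-3 set is used. Dated grade 2 events may need abstraction from charts, because the addendum in section 7.2 keeps events below grade 3 off the adverse event log and case report forms, although section 12.1.2 lists toxicities among the database entries. No increase in enrolment is needed.

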3.3 Rationale for Use in Treatment of Locally Progressive or Recurrent Disease

The development of recurrent pancreatic cancer after definitive treatment with surgery, radiation, chemotherapy, or a combination of these universally portends a dismal prognosis, with the 5-year survival for such patients being 5.6% or less (45). Unfortunately, this scenario is not uncommon; even among the small number of patients (10-15%) able to undergo potentially curative surgical resection, more than 80% subsequently develop recurrent disease (46). Among the majority of patients with pancreatic cancer who present with unresectable disease, chemoradiation is able to transiently stabilize the disease in some patients and to prolong median survival to 8-14 months (47-50). However, virtually 100% of patients develop disease progression and succumb within 3 years (51-55).

The pattern of recurrence in pancreatic cancer is well known (11,18,56,57) and is similar to that of periampullary adenocarcinoma (35). Following resection, 71-77% develop distant metastases within 2 years, often accompanied by concurrent locoregional recurrence, while up to 30% (58, 59) exhibit isolated locoregional recurrence (60,61). Patients who develop combined distant/locoregional recurrence have a median survival of 3 months from the time

of recurrence, while those with isolated locoregional recurrence have a median survival of 7 months (60). Locoregional recurrence is, therefore, a common and serious problem both in the setting of metastatic disease and as an isolated entity. Symptomatic manifestations include pain, gastric outlet/small bowel obstruction, portal hypertension, biliary obstruction, and malnutrition (61). Although survival is determined chiefly by systemic disease control, local control is an important factor contributing to quality of life (62,63). The symptoms associated with local recurrence require a mode of treatment that is swift and efficacious in order to restore patient quality of life and give patients the best chance at greater overall survival.

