We recently presented the preliminary results of our phase II multi-center trial of gemcitabine (GEM) and fractionated Linac based SBRT to determine if a high rate of LPFS with reduced toxicity could be achieved. After multidisciplinary review, 32 pts with locally advanced PDA received GEM in sequence with Linac based SBRT (6.6 Gy in 5 consecutive daily fractions, 33 Gy total). LPFS, metastasis free survival (MFS), and overall survival (OS) were measured from date of tissue diagnosis. Objective tumor response (OTR) was assessed by RECIST/PERCIST. EORTC QLQ-C30/PAN26 questionnaires were used to measure QOL. Median f-up was 12 mos (range, 2-23). Mean age was 69.9 yrs (SD, 9.8) and 62% were male. Patients received a mean of 2.2 (SD, 1.0) GEM doses prior to SBRT and 8.3 (SD, 5.6) doses total. All pts completed SBRT. Median OS was 15.9 months (95% CI, 12.7-18.8). Stratification by CA19-9 > or < 90 at diagnosis yielded a hazard ratio of 6.2 for > 90(p=0.021). Median LPFS has not been reached and median MFS was 10.2 mos (95% CI, 2.9-17.5). LPFS rate at 1 year was 87%. OTR on CT was seen in 41%, while 41% had stable disease and 18% progressed. Tumor metabolic activity decreased in 17/18 patients with pre/post- Linac based SBRT PET available. Mean peak SUV was 4.0 pre- Linac based SBRT versus 2.4 post-Linac based SBRT (p=0.002). Median CA19-9 was reduced from 124.7 prior to SBRT to 43.9 afterwards. Acute toxicity included: grade 2 anorexia (37%), fatigue (28%), nausea (22%), abd pain (19%), weight loss (9%), diarrhea (3%); gr 3 nausea (9%); and gr 4 nausea (6%). Late gr \geq 3 GI toxicity was seen in 9%. Mean QOL score 4 wks post-Linac based SBRT was similar to baseline (p=0.38). At 6 most here was a trend towards improved QOL (p=0.07). Overall, fractionated Linac based SBRT with GEM achieved high rates of LPFS and tumor response. Minimal grade ≥ 3 acute and late toxicity was observed. Linac based SBRT is more likely to benefit patients with Ca-19-9 <90. A combination of Linac based SBRT with more aggressive chemotherapy may further improve outcomes.

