11.1.6 Progression-Free Survival (or other parameters)

The criteria for time to progression and progression-free survival (PFS) will be the duration from Linac based SBRT treatment to documented local/regional or distant progression or death. Local PFS will be measured as the duration from Linac based SBRT treatment to local progression or death from any cause.

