12.2 Stopping Rules

All outcome data (toxicity and efficacy) will be reviewed every 6 months by the Principal Investigator and key Co-Investigators. This study will be monitored by the JHH IRB. All potential adverse events will be reported to the SKCCC Data Safety Monitoring Committee and the JHH IRB. An interim analysis is planned to assess late grade 2 or greater gastritis, enteritis, fistula, ulcer, or late grade 3 or greater GI toxicity when 16 patients are accrued. If 7 or more patients have late grade 2 or greater gastritis, enteritis, fistula, ulcer, or late grade 2 or greater gastritis, enteritis, fistula, ulcer, or late grade 2 or greater gastritis, enteritis, fistula, ulcer, or late grade 3 or greater GI toxicity within one year, the trial will be halted (note: accrual will continue while interim analysis is being conducted). After the first 16 patients are followed up for one year, we will also estimate the 1-year local progression free survival. If the upper bound of a two-sided 98% confidence interval (alpha = 0.02) of local progression free survival is below 30% in cohort A, or less than 50% in cohort B, the accrual at that cohort will be halted for lack of efficacy.

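### Cohort B's 65% target for 1-year LPFS, which counts deaths, lies above all five 1-year survival figures cited for SBRT-treated or locally recurrent patients, so mortality will dominate the LPFS result and the 80-90% local-control hypothesis needs another estimate

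*Combined protocol and SAP*

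**What the plan says.** - **Endpoint.** Section 11.1.6 times local PFS from SBRT "to local progression or death from any cause". Section 13.6 likewise counts death, and it takes 1-year local control from the Kaplan-Meier curve of this composite. It adds a cumulative incidence of local-regional progression with death competing, but no target or halt uses that estimate.
- **Targets.** Section 13.4.2 gives the LPFS comparison as "test the increase of 1-year local progression free survival from 30% to 45% in cohort A and 50% to 65% in cohort B". On power, the same section says "this sample size will reach 89% and 90% power". The inputs are 60 patients per cohort, one-sided 0.04, exponential times, 2.5 years of accrual and 1 year of follow-up. No source is given for the null or target values.
- **Halt.** After the first 16 patients have one year of follow-up, if the upper 98% limit for LPFS is below 30% (A) or 50% (B), section 12.2 says "the accrual at that cohort will be halted for lack of efficacy". Section 13.5 says accrual stops and the trial is re-evaluated.
- **Hypothesis.** The synopsis hypothesises 80-90% local control at one year.
- **Survival background.** For the single-fraction 25 Gy series, section 3.3 reports: "Overall survival at 6 and 12 months was 56% and 21%, respectively". For gemcitabine plus 25 Gy, section 3.2 reports that "the 1 year survival was 50" per cent. Section 3.3 adds that "those with isolated locoregional recurrence have a median survival of 7" months, a median of 8.65 months from SBRT in the three-fraction series, and a median of 15.9 months from diagnosis in the multi-center 33 Gy trial, where "Median LPFS has not been reached".

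**The concern.** A patient who dies within the year without local progression is an LPFS failure. In a disease where section 3.3 itself says survival depends mainly on systemic control, a composite that includes death can miss its target while the irradiated tumour stays controlled. The single-fraction 25 Gy series shows this without modelling: 84% were free of local progression at 12 months, inside the hypothesised range, yet with 21% alive its LPFS under this protocol's definition is at most 21%. If the trial saw the same, the plan would report failure on LPFS, and possibly a halt for lack of efficacy, although the local hypothesis was met. The stated 90% power would also give false reassurance about what 60 patients can show.

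**Working it through.** **1. The stated power reproduces.** Let λ = -ln(1-year LPFS). Expected events are d = 60 × [1 - (e^(-λ) - e^(-3.5λ)) / (2.5λ)]. Power = Φ{[ln(λ0/λ1) - 1.751/√d0] × √d1}, where 1.751 is the one-sided 0.04 normal quantile.
- Cohort B: λ0 = 0.693, λ1 = 0.431, d0 = 45.7, d1 = 36.1. (0.476 - 0.259) × 6.01 = 1.30, power 90.4%.
- Cohort A: λ0 = 1.204, λ1 = 0.799, d0 = 54.3, d1 = 48.3. Power 88.6%.

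The arithmetic is sound. The question is whether the target can be reached.

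**2. Survival ceiling.** LPFS ≤ OS at every time. Where only a median is given, 1-year OS = 0.5^(12/median). LPFS at 85% control = 0.85 × OS, taking local control as independent of survival. The chance of rejecting uses the formula in step 1 with λ1 from that LPFS.

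| Source | 1-year OS = LPFS ceiling | LPFS at 85% control | Chance B rejects 50% | Chance of B's interim halt |
|---|---|---|---|---|
| 25 Gy × 1 series (stated) | 21% | 17.9% | below 0.2% | 44-68% |
| Isolated local recurrence, median 7 months | 30.5% | 25.9% | below 0.2% | 18-37% |
| Three-fraction series, median 8.65 months | 38.2% | 32.5% | below 0.2% | 7-18% |
| Gemcitabine + 25 Gy (stated) | 50% | 42.5% | 0.05% | 1-4% |
| 33 Gy trial, median 15.9 months from diagnosis | 59.3% | 50.4% | 4.7% | 0.2-1.0% |

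- At OS 50%: λ1 = 0.856, d1 = 49.5. (-0.211 - 0.259) × 7.03 = -3.30, or 0.05%. A hazard-scale test gives 0.25%, with the same message.
- At OS 59%: λ1 = 0.686, d1 = 45.5. (0.011 - 0.259) × 6.75 = -1.67, or 4.7%. Control of 80% and 90% gives LPFS of 47% and 53%, and chances of 1.1% and 14.3%.
- With perfect control, the chance is 4% at OS 50% (LPFS equals the null) and about 46-56% at OS 59%, depending on the variance used.

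**3. Survival that the 65% target needs.** With perfect control, OS must be at least 65%, an exponential median of 12 × ln 2 / 0.431 = 19.3 months. With 90% control it is 0.65/0.90 = 72%, and with 80% control 0.65/0.80 = 81%.

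**4. Interim halt, cohort B.** The exact upper 98% limit is 43% at 2/16 and 50.3% at 3/16, so a halt needs 2 or fewer patients alive without local progression. Greenwood gives 41.5% at 3/16 and 50.2% at 4/16, so 3 or fewer. The ranges in the table are the binomial probabilities of at most 2 and at most 3 of 16.

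**5. Cohort A.** Against the 30% null, only the 21% figure is clearly lower, and the 7-month median is about equal to it. The 45% target is above three of the five figures and below the other two. A halt needs 0 (exact) or at most 1 (Greenwood) of 16. With perfect control that has probability 2-12% at OS 21% and 0.3-2.4% at OS 30%.

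**6. The earlier LPFS is a different quantity.** In the 33 Gy trial LPFS and OS were both dated from diagnosis. Had deaths counted, median LPFS could not exceed the 15.9-month median OS. It was not reached, so the 87% at 1 year there cannot have counted deaths.

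**The case against.** - **A reader might infer that cohort B cannot beat its null even with perfect local control.** The documents do not support that. The one cited series using cohort B's regimen converts to about 59%, and its confidence interval of 12.7-18.8 months converts to 52-64%, all above 50%. It is dated from diagnosis: taking 3 months off the median gives 52%, and 4 months gives 50%. This objection stands against the 50% null, though not against the 65% target.
- **A reader might infer that LPFS tests systemic death and not local effect.** That is too absolute. Local progression is still an event, and nulls of 30% and 50% are consistent with some allowance for death. What can be said is that mortality dominates.
- **The background series may not fit.** They are mostly locally advanced disease, and 19% of the 25 Gy series had metastases, which section 4.2.7 excludes. The plan names none of them as the basis for its nulls. This stands: actual survival may differ, and the 44-68% halt probability rests on the least well matched series.
- **Local effect is analysed elsewhere.** Sections 13.3 and 13.6 plan competing-risk analyses, LPFS is secondary, and the sample size rests on late toxicity. True, but the power statement and the halt use only the composite.
- **Replacing the halt with cumulative incidence would have its own fault.** Early deaths lower the cumulative incidence of local progression, so a cohort dying quickly could look controlled. This stands, and is why the fix keeps LPFS and reads the estimates together.

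**Conclusion.** The point holds for cohort B's target. All five cited figures for SBRT-treated or locally recurrent patients lie below 65% before any local failure is counted, and four lie at or below the 50% null; the 33 Gy trial at about 59% is the exception. With 85% local control, the chance of rejecting 50% is below 0.2% at OS of 50% or less and about 5% at OS 59%, against a stated 90%. The LPFS result would be driven mainly by mortality, and the endpoint tested is not the one behind the 87% benchmark.

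The interim halt is a lesser problem: it is likely only near the lowest survival figure, and has probability 1-4% at OS 50% and 1% or less at OS 59%. The case for cohort A is weak. It would be wrong to say that all the LPFS values equal or exceed the cited OS: cohort A's 30% exceeds only the 21% figure, its 45% is below 50% and 59%, and cohort B's 50% is below 59%.

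Assumptions: exponential survival where only a median is given; independence of local control and survival; complete one-year follow-up of the 16 interim patients. The ceiling itself needs neither independence nor a power model. The exponential conversion may be generous: from 56% at 6 months in the 25 Gy series it would predict 0.56² = 31% at 12 months, against the reported 21%. Section 3.3's 8-14 month medians after chemoradiation for unresectable disease convert to 35-55%, also below 65%. The longer medians in section 2 come from resected patients on adjuvant therapy and are not used here.

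**What to change.** 1. **Section 13.4.2.** State that cohort B's 65% target needs 1-year OS of at least 65% with perfect local control, and about 72-81% with 90-80% control. Restate the 90% power as conditional on that survival, and show power at LPFS values consistent with the cited OS (for example 0.05% at 42.5%, 4% at 50% and 14% at 53%).
2. **Section 13.6.** Judge the 80-90% local-control hypothesis on the planned 1-year cumulative incidence of local progression with death as a competing event, not on the LPFS curve. Report LPFS and OS beside it, since early deaths lower the cumulative incidence.
3. **Sections 12.2 and 13.5.** Require that cumulative incidence and OS be read alongside LPFS before a halt is labelled lack of efficacy, so that a halt driven by deaths without local progression is not reported as local failure.

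Do not add a sentence saying that every LPFS value equals or exceeds the cited OS.

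The cost is wording in the protocol and SAP. No new data or analyses are needed. The downside is that the 90% power becomes conditional and looks less favourable.
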